2.8. General Analysis Method

In general, continuous variables will be summarized using descriptive statistics such as mean, standard deviation (SD), median and range. Categorical variables will be summarized using frequency and percentage. For time-to-event variables, which is defined as from randomization to the date of the event, the Kaplan-Meier method will be used for descriptive summaries. For the calculation of time-to-event and duration-of-event variables, the difference between the start date and the end date plus 1 day will be used.

2.9. Analysis Sets

The following analysis sets are defined.

- Intent-to-treat (ITT): defined as subjects who have been randomly assigned to the DRd or Rd group. Analyses of demographics, baseline characteristics and efficacy endpoints will be primarily analyzed based on this population.
- Safety population: defined as subjects who have received at least 1 administration of any study treatment (partial or complete). This population will be used for all safety analyses. The safety analyses grouping will be according to treatment actually received.
- Response-evaluable: defined as subjects who have a confirmed diagnosis of multiple
 myeloma and measurable disease at baseline or screening visit. In addition, subjects must
 have received at least one administration of study treatment and have adequate postbaseline disease assessments. Measurable disease is defined as follows:
 - IgG myeloma: Serum monoclonal paraprotein (M-protein) level ≥1.0 g/dL or urine M-protein level ≥200 mg/24 hours; or
 - IgA, IgD, IgE or IgM multiple myeloma: serum M-protein level ≥0.5 g/dL or urine M-protein level ≥200 mg/24 hours; or
 - Light chain multiple myeloma without measurable disease in serum or urine: Serum immunoglobulin free light chain (FLC) level ≥10 mg/dL and abnormal serum immunoglobulin kappa lambda free light chain ratio.

This population will be used as sensitivity analyses for selective response-related secondary endpoints such as CR or better rate.

- Per-protocol (PP) population: defined as subjects who are randomized and meet all eligibility criteria.
- Pharmacokinetics-evaluable: is defined as subjects assigned to DRd group who received at least 1 administration of daratumumab and have at least 1 pharmacokinetic sample concentration value after the first infusion. All pharmacokinetics analyses are based on the pharmacokinetic evaluable population.
- Immune response-evaluable: is defined as subjects assigned to DRd group who have at least 1 immunogenicity sample obtained after their first daratumumab administration.
- Molecular genetic evaluable: defined as subjects who meet one of the following biomarker criteria for risk assessment based on the next generation sequencing (NGS) data:
 - Standard risk: subjects that are negative (=molecular aberration absent) for all del17p, t(14;16), t(4;14).
 - High risk: subjects that are positive (=molecular aberration present) for any of del17p, t(14;16), t(4;14).
- Cytogenetic evaluable: defined as subjects who meet one of the following cytogenetic risk categories:
 - Standard risk: subjects that are negative for del17p, t(14;16), t(4;14) by FISH/Karyotype.
 - High risk: subjects that are positive for any of del17p, t(14;16), t(4;14) by FISH/Karyotype.

2.10. Definition of Subgroups

The following pre-specified subgroup analyses are to be performed at the 2nd IA for the efficacy and safety endpoints (Table 1). Additional subgroup analyses may be performed, if requested and deemed necessary by IDMC for making their decision.

Table 1: Subgroup Analyses of Efficacy and Safety Endpoints

Subgroup	Definition	Analysis Type
Sex	Male, Female	E, S
Age	<75 years, ≥75 years	E, S
Race	White, Others	E, S
Baseline renal function (CrCl)	E: >60 mL/min, ≤60 mL/min S: <30, 30 to <60, 60 to <90, ≥90 mL/min	E, S
Baseline hepatic function	Normal, Impaired ^a	E, S
Region	North America, Others	E, S
International Staging System (ISS)	I, II, III	E
Type of MM	IgG, Non-IgG	E
Cytogenetic risk	High risk ^b , Standard risk	E
ECOG performance score	$0, 1, \ge 2$	E

E: efficacy (PFS, ORR, CR or better rate); S: TEAE

2.11. Other General Definitions

2.11.1. Treatment Emergent Adverse Events

Treatment emergent adverse events (TEAEs) are defined as any AE with onset date and time on or after that of the first dose of study drug infusion through 30 days after the last dose of study drug or the day prior to start of subsequent therapy, whichever is earlier; or any AE that is considered related to (probably, possibly, or very likely) study drug regardless of the start date of the event. AEs with missing or partial onset date and time will be considered as treatment-emergent unless the onset date and time of an AE can be determined as earlier than that of the first dose, or later than 30 days after last dose.

2.11.2. Linking of Treatment Emergent Adverse Events

All event records of the same preferred term from the same subject are to be linked by the onset date and the end date. If an event is followed by another event of the same preferred term with an onset date (or date/time) the same as or 1 day (or 1 minute if applicable) after the end date (or date/time) of the previous record and any features of the adverse event (i.e.: toxicity grades/seriousness/action taken) are different between these two records, these 2 records should be linked together and considered as 1 event, the maximal toxicity grade of the 2 records would be used for the analysis.

^a Includes mild (total bilirubin \leq ULN and AST > ULN or ULN < total bilirubin \leq 1.5 \times ULN), moderate (1.5 \times ULN < total bilirubin \leq 3 \times ULN), severe (total bilirubin > 3 \times ULN).

b. High risk is defined as positive for any of del17p, t(14:16) or t(4:14) by FISH/Karyotype.

3. SUBJECT INFORMATION

3.1. Demographics and Baseline Characteristics

Unless specified otherwise, all demographic and baseline characteristics variables will be summarized for the ITT population. No statistical comparison between the 2 treatment groups is planned.

The distribution of subject enrollment will be presented for each treatment group according to region and country.

Subject demographic and baseline characteristic variables: age (<65 years, 65 to <70 years, 70 to <75 years, and ≥75 years), sex, ethnicity, race, weight (kg), height (cm), body surface area (BSA, m²) and ECOG performance status will be summarized by treatment group and overall. A listing of subject demographic and baseline characteristics will be provided as well.

Baseline disease characteristics including type of multiple myeloma (IgG, IgA, IgM, IgD, IgE, light chain only, biclonal, or negative immunofixation), type of measurable disease (Serum only (IgG, IgA, Other - IgD, IgM, IgE and biclonal), Serum and urine, Urine only, Serum FLC only, or not evaluable), ISS staging at baseline (I, II, III), time since initial MM diagnosis (months), number of lytic bone lesions (None, 1-3, 4-10, more than 10), presence of diffuse myeloma-related osteopenia (Yes, No), number of extramedullary plasmacytomas ($0, \ge 1$), presence of extramedullary plasmacytomas (Yes, No), bone marrow biopsy/aspirate % plasma cells (0, 10 - 30, 0), bone marrow aspirate % plasma cells (0, 10 - 30, 0), bone marrow aspirate % plasma cells (0, 10 - 30, 0), standard-risk and high-risk cytogenetic abnormalities

(del17p, t(4;14), t(14;16)), will be summarized and tabulated by treatment group and overall.

A descriptive summary of selected hematology and biochemistry laboratory analytes at baseline will be provided for each treatment group and overall. In addition, baseline toxicity grade of each selected laboratory analyte in hematology and chemistry panel will be summarized by treatment group using frequency based on the safety population.

Medical history collected at baseline or screening visit will be summarized by system-organ class and preferred term for each treatment group and overall.

A summary of stratification factors (ISS staging, region, and age) used in the randomization based on IWRS will be provided to evaluate whether or not randomization process was appropriately executed in the study. The stratified log-rank test and stratified cox model use these stratification factors in randomization.

3.2. Disposition Information

An overview of subject disposition in the study will be provided. The overview includes a summary of total number of subjects who are randomized to each treatment group, the number

and percentage of subjects who are randomized but not treated in each treatment group, and total number of subjects who are treated in each treatment group. For all treated subjects (defined as subjects who have received at least 1 administration of any study treatment), the number and percentage of subjects who discontinued treatment including reason for discontinuation as indicated by the investigators will be summarized. The similar summaries will be presented for all randomized subjects who discontinued from study.

A list of subjects who discontinued study treatment will be provided for safety subjects. This listing will include subject ID, treatment group, date of treatment discontinuation, study day of last dose, reason for discontinuation as well as the specific adverse events (MedDRA preferred term/verbatim term) if discontinuation due to AEs and primary cause of death if discontinuation due to death. A similar list of subjects who discontinued study will be provided for ITT subjects.

3.3. Extent of Exposure

Extent of exposure to study treatments will be summarized and presented based on the safety population.

The number and percentage of subjects treated within each cycle will be summarized by treatment group. The maximum number of treatment cycles received for each subject will be summarized by frequency and descriptive statistics.

Duration of study treatment, defined as the number of months from the date of the first administration of study treatment to the date of the last administration of study treatment, will be summarized.

The number of daratumumab administrations will be summarized for subjects treated with DRd. The total dose administered for daratumumab (mg/kg), lenalidomide (mg), and dexamethasone (mg) will be summarized overall, by cycle of daratumumab treatment.

The dose intensity, which is defined as the sum of total dose administered in all cycles divided by the number of treatment cycles, will be calculated for each study treatment and summarized accordingly. Additionally, the daratumumab dose intensity will be summarized by cycles of daratumumab treatment.

The relative dose intensity (%) defined as the ratio of total actually received dose and total planned dose (planned dose level times the number of administered infusions/medications) will be calculated for each study treatment and summarized by treatment group using descriptive statistics.

The number of subjects with treatment dose delay within the cycle, dose reduced, dose re-escalated per protocol, or dose skipped for lenalidomide and dexamethasone will be summarized for each treatment group. The reasons (AE or other) for treatment dose delay within the cycle, dose reduced, dose re-escalated per protocol, or dose skipped for lenalidomide and dexamethasone will be reported. In addition, a summary of study treatment dose modifications by cycle will be provided.

16

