6.4. Dose Delays and Dose Modification

Subjects who need to discontinue treatment with any one component of study treatment (lenalidomide, dexamethasone, or daratumumab) may continue to receive treatment with the other components of study treatment, as assigned.

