6.4.1. Daratumumab Dose Modification

Dose modification of daratumumab is not permitted, but dose delay is the primary method for managing daratumumab-related toxicities.

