2. GENERAL ANALYSIS DEFINITIONS

2.1. Visit Windows

For analyses of data by cycle, if data are collected by date (e.g., AE onset), the corresponding study evaluations will be assigned to actual sequential cycles, which are derived from the study treatment administration data. The start date of a particular cycle is defined as the date of the first scheduled dose of any component of the study treatment, and the end date of a cycle is the start date of the next cycle minus 1. For the last cycle, the end date is defined as the end of treatment visit date or the minimum of last study treatment date plus 30 days and subsequent antimyeloma therapy minus 1 day, if the end of treatment visit date is not available.

In general, if data (e.g., laboratory and vital sign etc.) are collected by cycle, the nominal cycle will be used to summarize data. However, due to possible cycle delays, assessment performed in the same cycle may not be well aligned in time scale for different subjects.

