5.1.6. TEAEs Leading to Dose Modifications

Incidence of TEAEs leading to dose modifications will be summarized by MedDRA SOC and preferred term. The summaries will be presented by all grades and Grade 3 or 4 for each treatment. This table will include TEAEs leading to cycle delays or dose modification of at least 1 of the study treatments, the dose modifications include dose delay within the cycle, dose reduced (not applicable to daratumumab), dose re-escalated per protocol (not applicable to daratumumab), or dose skipped.

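### SAP 3.3 builds the relative dose intensity denominator from doses actually given, so an omitted dose never counts as a shortfall and the percentage is not the share of the planned regimen delivered

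*SAP*

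**What the plan says.** SAP 3.3 plans RDI for each study treatment, summarised by treatment group. The numerator is the dose actually received. The denominator is "total planned dose (planned dose level times the number of administered infusions/medications". The SAP does not say whether the planned dose level is the subject's assigned starting level or the level currently prescribed.

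The same section plans other exposure outputs:

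- dose intensity, defined as "the sum of total dose administered in all cycles divided by the number of treatment cycles", with the addition that "the daratumumab dose intensity will be summarized by cycles of daratumumab treatment";
- total dose, overall and by cycle, and the number of daratumumab administrations;
- counts of subjects with delayed, reduced, re-escalated or skipped doses, with reasons, for lenalidomide and dexamethasone only;
- a by-cycle table: "a summary of study treatment dose modifications by cycle will be provided".

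SAP 5.1.6 adds a table of "TEAEs leading to cycle delays or dose modification of at least 1 of the study treatments". SAP 2.1 fixes what a treatment cycle is: "The start date of a particular cycle is defined as the date of the first scheduled dose of any component of the study treatment".

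On dosing, Protocol 6.4.1 states: "Dose modification of daratumumab is not permitted". Under Protocol 6.4.1.1, a daratumumab dose outside its window is missed and not replaced, while the first-day dose of a cycle is to be delayed rather than left out. Protocol 6.2 and 6.3 allow missed lenalidomide and dexamethasone doses to be skipped. Table 5 of Protocol 6.4.2.2 includes a route in which lenalidomide is interrupted and then resumed at the starting dose. Under Protocol 6.4, a subject who stops one component "may continue to receive treatment with the other components of study treatment, as assigned".

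**The concern.** The number of doses administered is an outcome, not a plan. With that number in the denominator, an omission removes the same planned amount from the comparison that it removes from delivery, and no shortfall is registered. For daratumumab, omission is a main route by which delivery can fall below plan, because the dose itself cannot be modified; the row cannot see it.

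RDI is also the only output in SAP 3.3 that sets dose received against dose planned. Someone reading 100% in a table labelled relative dose intensity is likely to take it that the planned regimen was given. What is at stake is the description of exposure, and with it the context in which tolerability is read. The issue remains live because Protocol 9.1.8 plans a final study report that updates efficacy and safety.

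**Working it through.** **Inputs.** Daratumumab: weekly in Cycles 1-2, every other week in Cycles 3-6, every 4 weeks from Cycle 7, at 16 mg/kg IV (SAP 1.1; Protocol 6.1.2). Lenalidomide: Days 1-21 of 28, at 25 mg, or 10 mg with reduced renal function (Protocol 6.2). Dexamethasone: weekly, at 40 mg, or 20 mg for subjects older than 75 or underweight (Protocol 6.3). The documents give no omission rates, so every number of omitted doses below is an assumption.

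**The plan's own figure.** Over 13 cycles of 28 days: 4×2 + 2×4 + 1×7 = 23 doses. Consecutive weeks at the start: 8 plus Cycle 3 Day 1 = 9. Both match SAP 1.1.

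**Formulas.** Let L be the planned level, A the doses given and S the doses scheduled.

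- RDI as written = dose received / (L × A)
- Share of schedule delivered = dose received / (L × S)

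If every dose given equals L, the first is L×A/(L×A) = 100% for any A, and the second is A/S.

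**Daratumumab, first year.** Doses not on Day 1: 3 per cycle in Cycles 1-2 and 1 per cycle in Cycles 3-6, so 3×2 + 1×4 = 10. These can clearly be omitted under Protocol 6.4.1.1. Table 3 is less clear for Cycle 7 onward.

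| Omitted (assumed) | Share delivered | RDI as written |
|---|---|---|
| 2 of 23 | 21/23 = 91.3% | 100% |
| 4 of 23 | 19/23 = 82.6% | 100% |
| 6 of 23 | 17/23 = 73.9% | 100% |

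The 100% is approximate in practice. Infusions may be incomplete, weight is rounded to the kilogram, and the dose is recalculated only after a weight change of more than 10% (Protocol 6.1.2).

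**Lenalidomide, 1 of 6 cycles held, resumed at 25 mg.** A full cycle is 21×25 = 525 mg. Received: 5×525 = 2625 mg. Written: 2625/2625 = 100%. Scheduled: 2625/(6×525) = 2625/3150 = 83.3%. Dose intensity does fall, to 2625/6 = 437.5 mg per cycle against 525, because a cycle started by another component still counts under SAP 2.1.

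**Dexamethasone, 1 of 4 weekly doses omitted.** Written: 120/120 = 100%. Scheduled: 120/160 = 75.0%.

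**Reduced levels depend on the undefined term.** Take three cycles at 25 mg, one held and two at 15 mg: received 3×525 + 2×315 = 2205 mg.

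- Planned level = starting level: written 2205/(5×525) = 84.0%, against 2205/3150 = 70.0% of the starting-level schedule.
- Planned level = level currently prescribed: written 2205/2205 = 100%.

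Take one cycle at 25 mg and one at 15 mg. On the starting-level reading, RDI is 840/1050 = 80.0% with nothing omitted. It becomes 630/700 = 90.0% if 14 of the 15 mg days are omitted, while delivery falls to 630/1050 = 60.0%. On the current-level reading RDI is 100% both times.

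**The case against.** The strongest reply is that the SAP states its formula openly, the row is descriptive, and omissions are visible elsewhere. Much of that stands. Dose intensity divides by treatment cycles and so falls with skipped doses and wholly held components. Lenalidomide and dexamethasone skips are counted by arm with reasons. SAP 5.1.6 picks up delays and skips linked to adverse events. For IV daratumumab, the by-cycle dose intensity can be set by hand against 64, 32 and 16 mg/kg (4, 2 and 1 doses of 16), though not after a switch to the fixed SC dose. For lenalidomide and dexamethasone a percentage cannot be recovered from group summaries, because full delivery is 525 or 210 mg and 160 or 80 mg per cycle depending on the subject. Mean mg per cycle can still be compared between arms, since randomisation should give a similar mix of starting doses. A reader might infer that the exposure section hides omissions altogether, or conceals a difference between arms. The documents do not support that; what is missing is a percentage of plan.

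A reader might also infer that omitting doses at a reduced level raises RDI. That follows only if the planned level means the starting level, which the SAP does not say.

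Finally, a schedule-based RDI would not show everything either. Delay is the protocol's main way of managing daratumumab toxicity, and a delayed cycle counted once still gives 100%. That is a fair limit on the fix and should be stated in the table.

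**Conclusion.** The point holds for the RDI row. As defined, it cannot register an omitted dose as a shortfall, and for daratumumab it stays near 100% whatever number of doses is missed. The gap between delivery and RDI is 17.4 percentage points for 4 of 23 daratumumab doses (100 − 82.6), 16.7 for 1 of 6 lenalidomide cycles held (100 − 83.3) and 25.0 for 1 of 4 dexamethasone doses (100 − 75.0). These sizes rest on assumed omissions with the remaining doses given at the planned level; how often omissions occur is not in the documents. Statements about reduced dose levels are conditional on a definition that the SAP leaves open.

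Severity is minor. PFS, OS, the alpha allocation and the sample size do not use RDI, and it would be wrong to infer that any efficacy conclusion is affected.

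**What to change.** In SAP 3.3, define total planned dose as planned dose level times the number of administrations scheduled by protocol for that component, over the treatment cycles from its first dose to its permanent discontinuation or the data cut-off. State that:

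- the planned level is the protocol-assigned starting level, with protocol-specified renal changes in level or frequency (Protocol 6.2 and Table 6) applied to the plan;
- cycles in which the component was wholly held are included;
- no lenalidomide or dexamethasone doses are planned in Arm B during a gap caused by the earlier 24-month stop (Protocol 6.2 and 6.3).

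Add a footnote that RDI does not reflect cycle delays.

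Cost: one SAP paragraph and some subject-level derivation, because SAP 3.3 records modification reasons only as adverse event or other, which does not separate renal changes. RDI values become lower, and the row is no longer comparable with exposure tables from the earlier cut-off unless both versions are shown.

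Minimum alternative: keep the formula and relabel the row *average dose per administration relative to planned level*. That removes the misreading without reprogramming, but leaves no percentage of plan.

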3.4. Protocol Deviations

Major protocol deviations will be summarized for the ITT population by the following types (not limited) of deviation for each treatment group:

- Developed withdrawal criteria but not withdrawn
- Entered but did not satisfy criteria
- Received a disallowed concomitant treatment
- Received wrong treatment or incorrect dose
- Efficacy assessment deviation
- Safety assessment deviation

A listing of subjects with major protocol deviations including subject ID, type of deviation, and reasons for deviation will be provided.

3.5. Prior, Concomitant and Subsequent Therapies

With the study population of newly diagnosed multiple myeloma subjects who are not candidates for high dose chemotherapy and ASCT, prior systemic use of corticosteroids is limited to a short course (equivalent of dexamethasone 40mg/day for 4 days) for purposes other than multiple myeloma. If any, a listing of all prior systemic use of corticosteroids will be provided.

Concomitant medications collected in the CRF page during the study will be summarized by therapeutic class, pharmacologic class, and drug name for each treatment group. A similar summary will be provided for subjects who received growth factor support, pre-infusion medication and post-infusion medication, respectively. In addition, systemic steroids as concomitant medication use during the study will be summarized. Additionally, prophylactic antiviral medication use will be tabulated.

The total number of subjects who received subsequent antimyeloma therapy will be reported for subjects in safety population in each treatment group. A summary of subsequent antimyeloma therapy will be presented by therapeutic class, pharmacologic class and drug name. In addition, for subjects who received subsequent antimyeloma therapy, their best response to the first subsequent antimyeloma therapy will be summarized.

